**B. What medication are you on currently?**

| Name of drug | Dose | Frequency | Newly started within the past 2-3 days (Y/N) |
|--------------|------|-----------|--|
|              |      |           |  |
|              |      |           |  |

**C. Have been taking your starch as instructed? Y/N**

**If No, could you let us know why?**

**D. Have you experienced any side effects from the starch? Y/N**

**If yes, could you tell us about your symptoms?**

**This concludes the questionnaire. You will be contacted every 2 days to review your symptoms. If you have questions regarding your health or diagnosis of COVID-19, please contact your healthcare provider.**

## Appendix B: Instruction which will be sent to patient with the study treatment

[figure not shown]
[figure not shown]
Dear Study Participant,

Please take two tablespoons of the delivered starch once daily for three days. On the fourth day, please start taking two tablespoons of the delivered starch twice daily until day number 14.

You can place the starch in any cool substance such as water, juice, or applesauce to make it more palatable. Please stir constantly while drinking and some residue may form on the bottom without stirring.

Of note, it is not essential that you space out the two tablespoons by 12 hours, if you prefer you can take all 4 tablespoons at the same time.

Please repeat the above steps for 14 days. By the end of 14 days you should have completed all the bag starch content.

We thank **YOU** for volunteering to participate in this study during such a difficult time for the whole world. We are working together to fight this pandemic, and we thank you for being the most integral part of this fight. Your contribution to science will help us win this fight. We wish you health and a speedy recovery.

Sincerely,  
Study Team

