## Treatment Dosage and Administration

RPS or placebo will be administered at ~20 grams (2 tablespoons) once daily for days 1-3 and then twice daily for days 4-14, (**Table 2**).

Intervention and Placebo:

**Table 2.** Intervention and Placebo

|              |                                    |   |
|--------------|------------------------------------|---|
| Intervention | Study Product, Dose, Route Regimen | Food Source (used as a drug): Potato based dietary starch, Bob's Red Mill®, ~20 grams (2 tablespoons) orally twice daily. (start with 2 tablespoons once daily for 3 days, followed by twice daily on days 4 to 14 to minimize GI symptoms) |
|              | Duration of Administration         | 14 days   |
| Placebo      | Study Product, Dose, Route Regimen | Food Source (used as a drug): Corn based dietary starch by Bob's Red Mill, ~20 grams (2 tablespoons) orally twice daily. (start with 2 tablespoons once daily for 3 days, followed by twice daily on days 4 to 14)                          |
|              | Duration of Administration         | 14 days   |

- Storage and stability: Avoid extremes of temperature. No need for refrigeration.
- Preparation and Dispensing: Mix 2 tablespoons of dietary starch (~20 grams) with any amount water, juice, applesauce or any other cool substance to make palatable. Starch substance should not be heated or warmed.
- Other administration instructions: No regulation for administration of starch with or without other food or medications. As this is a commercially available food product, subjects can keep any remaining product at the end of study. We will determine compliance via questionnaire that will be utilized during phone follow ups (**see attached questionnaire**). Doses should be administered twice daily. Although we suggest the doses be spread apart to minimize any potential GI disturbance, there is no limit as to how closely together doses can be given. For example, doses do NOT need to be given 12 hours apart and instead can be given at times that feel comfortable to the subject.
- Missed doses should be documented by the research team during phone follow up
- Missed doses should simply be skipped with no need to make up this dose at a later time.
- Availability: Commercially Available

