| Adverse events related to
Resistant Potato Starch (RPS) | 
 
• Allergy to potato or corn based starch
 
• Persistent* Abdominal cramping or pain
 
• Nausea or vomiting
 
• Diarrhea
 
• Persistent Bloating
 
• Persistent Flatulence
 
 | All will be reported within 1 to 5 days to safety monitoring coordinator of event becoming known to PI at each site. |
|--|--|--|

\*Persistent symptoms will be defined as lasting 72 hours or longer

- If persistent side effects related to the investigational agent occur, a dose reduction can be made to once daily instead of twice daily dosing at the discretion of the PI or Co-I. If intolerance continues, despite decreasing the frequency of dosing, the investigational agent may be held for up to 3 days. Investigational agent can also be held for up to 3 days if the patient is unable to take oral intake for any reason. If investigational agent is held longer than 3 days, subject will be removed from treatment and included with an intention to treat protocol.
- The study intervention will be discontinued if patient meets the primary study endpoint of hospitalization

The Placebo uses corn starch. A potential risk although rare is allergy to corn. We will in screening ask about the potential subjects' exposure to corn and any reaction or avoidance of corn. Allergies to corn are extremely rare and there are no recent literature documenting specific rates, but one study from 1950 showed a very low rate of 0.16% (DOI:[https://doi.org/10.1016/0021-8707\(50\)90098-0](https://doi.org/10.1016/0021-8707(50)90098-0)).

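### The mailed instruction sheet expects an empty bag by day 14, while the protocol skips missed doses and lets participants keep leftovers; anyone who misses, reduces or holds doses cannot satisfy both

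*Combined protocol and SAP*

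**What the plan says.** Appendix B is the printed direction sent with the product. It gives the same step-up schedule as Table 2 ("start with 2 tablespoons once daily for 3 days, followed by twice daily on days 4 to 14 to minimize GI symptoms") and then adds: "By the end of 14 days you should have completed all the bag starch content". Its readable text does not mention missed doses or leftover product.

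The body of the protocol says something else on both. Treatment Dosage and Administration, like Drug Information, states: "Missed doses should simply be skipped with no need to make up this dose at a later time". It also says that "subjects can keep any remaining product at the end of study". Toxicities and Dosing Delays/Dose Modifications adds that for persistent side effects "a dose reduction can be made to once daily instead of twice daily dosing at the discretion of the PI or Co-I", and that the agent may be held for up to 3 days.

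On temperature, the protocol has an explicit prohibition: "Starch substance should not be heated or warmed". The sheet's readable text has only: "You can place the starch in any cool substance such as water, juice, or applesauce to make it more palatable".

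The packaging section gives the shipped amounts as 600 g of potato starch and 500 g of corn starch. Compliance is to be determined by questionnaire during the phone calls, and staff are to document missed doses at those calls. In Appendix A, the only scripted adherence item is part C: "Have been taking your starch as instructed? Y/N". A reason is requested only after a No. Sections 13 and 14 define interim feasibility as more than 60% of patients taking at least 50% of their prescribed doses.

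**The concern.** All contact in this trial is by phone and record review, so the mailed sheet is the text a participant has in hand when measuring a dose. If it sets an empty bag as the target while the protocol expects skipped doses to stay untaken, some participants may take extra or larger portions to reach that target. The participants affected would be those who missed, reduced or held doses, including those who did so because of gastrointestinal symptoms.

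Two things are at stake. The first is whether the intervention taken at home is the one the protocol describes. The second is the adherence record: someone who made up doses to finish the bag has followed the sheet and can truthfully answer Yes to part C. The feasibility criterion needs a proportion of doses taken, and the scripted answers do not supply one.

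**Working it through.** **Inputs.** Schedule: Table 2, repeated in Appendix B. Nominal dose: about 20 g per 2 tablespoons (Treatment Dosage and Administration). Potato label weight: 12 g per tablespoon (nutritional label under Drug Information), so 24 g per dose. Corn: Section 1 gives label calories per 8 g; that this is one tablespoon is an assumption, so I use 8 to 10 g per tablespoon, or 16 to 20 g per dose. Bags: 600 g potato, 500 g corn.

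**Number of doses.** 3 days × 1 + 11 days × 2 = 25.

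**Reproducing the bag weights.** Potato at label weight: 25 × 24 g = 600 g. Corn at the nominal dose: 25 × 20 g = 500 g. Each bag reproduces exactly under one of the documents' own conventions, but no single convention gives both. The nominal 20 g gives 500 g and 500 g; label weights give 600 g and, under the 8 g assumption, 25 × 16 g = 400 g.

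**Left in the bag (bag weight minus doses taken × grams per dose).** The hold column assumes a permitted 3-day hold during twice-daily dosing: 3 × 2 = 6 doses skipped, 19 taken.

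| Product | g per dose | Full adherence | After 3-day hold |
|---|---|---|---|
| Potato, 600 g | 24 (label) | 600 − 600 = 0 g | 600 − 456 = 144 g |
| Potato, 600 g | 20 (nominal) | 600 − 500 = 100 g | 600 − 380 = 220 g |
| Corn, 500 g | 20 (nominal) | 500 − 500 = 0 g | 500 − 380 = 120 g |
| Corn, 500 g | 16 (assumed) | 500 − 400 = 100 g | 500 − 304 = 196 g |

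The six skipped doses themselves weigh 6 × 24 = 144 g of potato starch at label weight, or 6 × 20 = 120 g at the nominal dose. The 220 g in the second row is those 120 g plus the 100 g left even with full adherence. Each day of reduction from twice to once daily leaves one further dose.

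**Side by side.** After any skipped dose there is starch left under every row. Emptying the bag by day 14 then requires either taking skipped doses later, which the skip rule excludes, or using portions larger than 2 tablespoons. Leaving the starch unused follows the protocol and misses the sheet's target.

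**By arm.** With full adherence, the surplus is in the potato bag only if both products are dosed at 20 g (100 g, or 5 doses). It is in the corn bag only if potato is 24 g and corn 16 g per dose (100 g, or 100 / 16 = 6.25 doses). It is in neither if potato is 24 g and corn 20 g. The documents do not settle which applies.

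**Adherence record.** The 50% bar is 0.5 × 25 = 12.5 doses, so 13 doses pass (52%) and 12 do not (48%). A participant who took 12 doses on schedule and made up one falls on either side, depending on how the made-up dose is counted. A series of Yes answers shows neither the count nor the made-up dose.

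**The case against.** The sheet never tells anyone to make up a dose. It gives the schedule, says to repeat it for 14 days, and then describes an end state that is correct for full adherence with potato at label weight and corn at 20 g. That stands: a reader might infer that the sheet orders catch-up dosing, and its text does not. The sheet still offers nothing for the participant who has not been fully adherent, and the protocol's rule for that case is missing from its readable text.

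Participants are also not left alone with the sheet. Calls come every 2 days during treatment, dose reduction goes through an investigator, staff must document missed doses, and treatment deviations are recorded. This limits the risk without removing it, because part C has no prompt for missed or made-up doses after a Yes. The item would be coarse whatever Appendix B said; the conflict adds uncertainty about which instruction it refers to.

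On temperature, a reader might infer that participants are never told to avoid heat. The documents do not support that. The instruction to use a cool vehicle carries part of the rule, two figures in Appendix B are not shown, and the package label text is not reproduced. Only the absence of the explicit prohibition from the readable text can be stated.

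The safety argument is thin: the protocol sets no limit on how close together doses may be taken, and the sheet allows all 4 tablespoons at once. No intake threshold is given that catch-up would breach.

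**Conclusion.** The contradiction between the empty-bag sentence and the rules on skipping doses, keeping leftovers, reductions and holds is real, and it applies to every participant who misses, reduces or holds a dose. For a 3-day hold during twice-daily dosing, the skipped doses amount to 144 g of potato starch at label weight or 120 g at the nominal dose. At the nominal dose there is also a surplus of 100 g in the potato bag and none in the corn bag with full adherence. The direction of any difference between arms depends on the tablespoon weight, and for corn on an assumption.

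A reader might go further and conclude that exposure and reported adherence do depart from the protocol, or that one of the bag weights is wrong. Neither follows. The documents give no frequency for catch-up intake, and each bag reproduces under one stated convention. What they support is a risk of unknown size to exposure at home and to the dose counts behind the feasibility criterion. The primary comparison is by intention to treat; its test, alpha and sample size are unaffected. This is an inconsistency worth correcting because correction is cheap, and it does not threaten the primary analysis.

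**What to change.** Reconcile Appendix B with Drug Information, Treatment Dosage and Administration, the bag weights in the packaging section, and the dose-modification text, so that the sheet and the protocol give the same direction on missed doses, leftover product and temperature. Which rule should prevail is for the sponsor; this review does not choose one. In the same revision, state the tablespoon weight assumed for each product, so that the bag contents and the sheet agree in both arms.

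Add one item to part C of the phone script: the number of doses taken and missed since the last call, and whether any were made up. With calls every 2 days, the participant has to recall at most 2 × 2 = 4 scheduled doses, and the 50%-of-doses criterion can then be computed from recorded counts.

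Cost: a one-page reprint, one script line and an IRB amendment. Enrolment and the primary analysis do not change.

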## Appendix C: Potato starch product specification

Original draft: 2/18/2016  
Revision date: 1/7/2020  
Approved by: [name]

Revised by: [name]  
Revision #: 11  
Document #: FG SPEC 1444 GF POTATO STARCH

### BOB'S RED MILL NATURAL FOODS, INC.

#### Product Specification

Product Name: GF POTATO STARCH

Product Number: 1444

Product Description: GF POTATO STARCH are made from starch that has been extracted from potatoes, processed in accordance with 21 CFR Part 117 subpart B and in compliance with state and federal requirements for food safety and quality.

Ingredients: Potato Starch.

Allergens: No Allergens. Manufactured in a facility that also uses tree nuts and soy.

Gluten Free: This product is a gluten-free food. In accordance with the Codex Alimentarius' established threshold for gluten contamination, this product contains less than 20 ppm gluten.

#### Physical Properties

Appearance: White powder.

Aroma: Neutral with no rancid or off-odors.

Flavor: Clean with no rancid or undesirable flavors.

BOB'S RED MILL NATURAL FOOD, INC.

Manufacturers of

Natural Stone Ground Whole Grain Flours • Cereals • Meals • Bulk Grains • Seeds • Beans  
[name] • [contact] • [contact] • [www.bobsredmill.com](http://www.bobsredmill.com)

Original draft: 2/18/2016  
 Revision date: 1/7/2020  
 Approved by: [name]

Revised by: [name]  
 Revision #: 11  
 Document #: FG SPEC 1444 GF POTATO STARCH

| Nutrition Facts  |                |
|---|----------------|
| Serving size  | 100g           |
| Amount per serving  |                |
| Calories   | 327.00  |
|   | % Daily Value* |
| Total Fat 0.00g   | 0%             |
| Saturated Fat 0.00g   | 0%             |
| Trans Fat 0.00g   |                |
| Cholesterol 0.00mg  | 0%             |
| Sodium 38.70mg  | 2%             |
| Total Carbohydrate 81.80g   | 30%            |
| Dietary Fiber 0.00g   | 0%             |
| Total Sugars 0.00g  |                |
| Includes 0.00g Added Sugars   | 0%             |
| Protein 0.00g   |                |
| Vitamin D 0.00mcg   |                |
| Calcium 18.20mg   |                |
| Iron 0.48mg   |                |
| Potassium 60.00mg   |                |
| * The % Daily Value (DV) tells you how much a nutrient in a serving of food contributes to a daily diet. 2,000 calories a day is used for general nutrition advice. |                |

BOB'S RED MILL NATURAL FOOD, INC.

Manufacturers of

Natural Stone Ground Whole Grain Flours • Cereals • Meals • Bulk Grains • Seeds • Beans  
 [name] • [contact] • [contact] • [www.bobsredmill.com](http://www.bobsredmill.com)

Original draft: 2/18/2016  
Revision date: 1/7/2020  
Approved by: [name]

Revised by: [name]  
Revision #: 11  
Document #: FG SPEC 1444 GF POTATO  
STARCH

#### Certifications

Kosher: Certified by OK Kosher Certification of Brooklyn, New York

Non-GMO: Verified by the Non-GMO Project.

3rd Party Food Safety Audit: Certified by NSF International, Safe Quality Food (SQF) Level II, Food Safety Code for Manufacturing Edition 8.0

Country of Origin: Germany, Netherlands, United States of America

Shelf Life: When handled under recommended storage, the product has a 730 day shelf life for optimum flavor and quality. Shelf life is printed on each package and case using a "Best By" date. The "Best By" date is the production date plus the determined appropriate shelf life time. The "Best By" date is displayed as Day/Month/Year and is printed with the format of DD/MM/YYYY

## Appendix D: Corn starch product specification

Original draft: 2/18/2016  
Revision date: 1/3/2020  
Approved by: [name]

Revised by: [name]  
Revision #: 5  
Document #: FG SPEC 1146 GF CORN STARCH

### BOB'S RED MILL NATURAL FOODS, INC.

#### Product Specification

Product Name: GF CORN STARCH

Product Number: 1146

Product Description: GF CORN STARCH are made from endosperm of corn kernels, processed in accordance with 21 CFR Part 117 subpart B and in compliance with state and federal requirements for food safety and quality.

Ingredients: Cornstarch.

Allergens: No Allergens. Manufactured in a facility that also uses tree nuts and soy.

Gluten Free: This product is a gluten-free food. In accordance with the Codex Alimentarius' established threshold for gluten contamination, this product contains less than 20 ppm gluten.

#### Physical Properties

Appearance: Fine white powder.

Aroma: Clean and fresh with no rancid or off-odors.

Flavor: Clean and fresh with no rancid or undesirable flavors.

BOB'S RED MILL NATURAL FOOD, INC.

Manufacturers of

Natural Stone Ground Whole Grain Flours • Cereals • Meals • Bulk Grains • Seeds • Beans  
[name] • [contact] • [contact] • [www.bobsredmill.com](http://www.bobsredmill.com)

Original draft: 2/16/2016  
 Revision date: 1/3/2020  
 Approved by: [name]

Revised by: [name]  
 Revision #: 5  
 Document #: FG SPEC 1146 GF CORN STARCH

| Nutrition Facts      |               |
|-----------------------------|---------------|
| Serving size                | 100g          |
| Amount per serving          |               |
| Calories             | 362.00 |
| % Daily Value*              |               |
| Total Fat 1.00g             | 1%            |
| Saturated Fat 0.40g         | 2%            |
| Trans Fat 0.01g             |               |
| Cholesterol 0.00mg          | 0%            |
| Sodium 0.00mg               | 0%            |
| Total Carbohydrate 87.80g   | 32%           |
| Dietary Fiber 1.30g         | 5%            |
| Total Sugars 0.00g          |               |
| Includes 0.00g Added Sugars | 0%            |
| Protein 0.70g               |               |
| Vitamin D 0.00mcg           |               |
| Calcium 14.60mg             |               |
| Iron 0.00mg                 |               |
| Potassium 1.18mg            |               |

\* The % Daily Value (DV) tells you how much a nutrient in a serving of food contributes to a daily diet. 2,000 calories a day is used for general nutrition advice.

BOB'S RED MILL NATURAL FOOD, INC.

*Manufacturers of*

Natural Stone Ground Whole Grain Flours • Cereals • Meals • Bulk Grains • Seeds • Beans  
 [name] • [contact] • [contact] • [www.bobsredmill.com](http://www.bobsredmill.com)

Original draft: 2/16/2016  
Revision date: 1/3/2020  
Approved by: [name]

Revised by: [name]  
Revision #: 5  
Document #: FG SPEC 1146 GF CORN STARCH

**Certifications**

Kosher: Certified by OK Kosher Certification of Brooklyn, New York

3rd Party Food Safety Audit: Certified by NSF International, Safe Quality Food (SQF) Level II, Food Safety Code for Manufacturing Edition 8.0

Country of Origin: Mexico, United States of America

Shelf Life: When handled under recommended storage, the product has a 730 day shelf life for optimum flavor and quality. Shelf life is printed on each package and case using a "Best By" date. The "Best By" date is the production date plus the determined appropriate shelf life time. The "Best By" date is displayed as Day/Month/Year and is printed with the format of DD/MM/YYYY

